4.2 Exclusion Criteria

Subjects will be ineligible for the study if they fulfill any of the following criteria:

1. Discontinued assigned study drug during the qualifying study for any reason including an adverse event or serious adverse event.
2. Female subject is not willing to use an acceptable method(s) of effective birth control during treatment with investigational product (IP) and for an additional 15 weeks after the end of treatment with IP. Female subjects, who have had a hysterectomy, bilateral salpingectomy, bilateral oophorectomy, or who are postmenopausal, are not required to use contraception
 - Menopause is defined as 12 months of spontaneous and continuous amenorrhea in a female \geq 55 years old; or age $<$ 55 years but no spontaneous menses for at least 2 years; or age $<$ 55 years and spontaneous menses within the past 1 year, but currently amenorrheic (eg, spontaneous or secondary to hysterectomy), and with postmenopausal gonadotropin levels (luteinizing hormone and follicle stimulating hormone levels $>$ 40 IU/L) or postmenopausal estradiol levels ($<$ 5 ng/dL) or according to the definition of "postmenopausal range" for the laboratory involved.
 - **Acceptable methods of effective birth control include: sexual abstinence (when this is in line with the preferred and usual lifestyle of the subject [periodic abstinence (eg, calendar, ovulation, symptothermal, post-ovulation methods), declaration of abstinence for the duration of a trial, and withdrawal are not acceptable methods of contraception]), surgical contraceptive methods (vasectomy or bilateral tubal ligation), use of hormonal birth control methods (pills, shots, implants or patches), intrauterine devices (IUDs), or two (2) barrier methods (each partner must use one barrier method) with spermicide – males must use a condom with spermicide; females must choose either a diaphragm with spermicide, OR cervical cap with spermicide, OR contraceptive sponge with spermicide. Note: Additional medications given during treatment with evolocumab may alter the contraceptive requirements. These additional medications may require an increase in the number of contraceptive methods and/or length of time that contraception is to be utilized after the last dose of protocol-required therapies. The investigator is to discuss these contraceptive changes with the study subject.**

3. Female subject is pregnant or breast feeding, planning to become pregnant or planning to breastfeed during treatment with IP and/or within 15 weeks after the end of treatment with IP.
4. Unreliability as a study participant based on the investigator's (or designee's) knowledge of the subject (eg, inability or unwillingness to adhere to the protocol).
5. Disorder that would interfere with understanding and giving informed consent or compliance with protocol requirements.
6. Have an unstable medical condition, in the judgment of the investigator.
7. Subject's medical condition requires lipid measurement and/or adjustment of background lipid-regulating therapy during the first 12 weeks of study participation.
8. Known sensitivity to any of the products to be administered during dosing.
9. Currently enrolled in another investigational device or drug study (excluding AMG 145 parent study), or less than 30 days since ending another investigational device or drug study(s), or receiving other investigational agent(s).

5. SUBJECT ENROLLMENT

Before subjects may be entered into the study, Amgen requires a copy of the site's written independent ethics committee and/or institutional review board (IEC/IRB) approval of the protocol, ICF, and all other subject information and/or recruitment material, if applicable (see [Section 11.2](#)). All subjects must personally sign and date the ICF before commencement of study specific procedures. A subject is considered enrolled once they have completed their end of study visit in the parent protocol and have signed the ICF.

All subjects who enter the study will keep the same subject identification number from the parent study. Each site participating in this study will be assigned a different site number from the parent study.

6. TREATMENT PROCEDURES

AMG 145 will be the investigational medicinal product (IMP) in this study.

The medical devices used in this study are the: prefilled autoinjector/pen (AI/Pen) and the 3.5 mL Personal Injector (when available).

An Investigational Product Instruction Manual (IPIM) containing detailed information regarding the storage, preparation, and administration of the investigational medicinal product will be provided separately.

6.1 AMG 145

AMG 145 will be manufactured and packaged by Amgen Inc. and distributed using Amgen clinical IP distribution procedures.

AMG145 will be presented as a sterile, preservative-free solution in a single use, disposable, handheld mechanical (spring-based) 1.0 mL prefilled auto-injector/pen (AI/Pen) or 3.5 mL Personal Injector (Personal Injector) for fixed dose, subcutaneous injection. The prefilled AI/Pen contains a 1.0 mL deliverable volume of 140 mg/mL AMG 145 in [CCI] mM proline, [C] mM acetate, [CCI] % (w/v) polysorbate 80, pH [CC]. The Personal Injector with prefilled cartridge assembly is a single-use, disposable, on-body electro-mechanical injection device that is co-packaged with a prefilled Crystal Zenith (CZ) cartridge assembly containing 3.5 mL deliverable volume of 120 mg/mL AMG 145 in [CCI] mM proline, [C] mM acetate, [CCI] % (w/v) polysorbate 80, pH [CC].

The 3.5 mL Personal Injector will only be made available for use in this study once it has been determined that the intended user population for AMG 145 can safely and effectively use the device in clinical trials under the guidance of the study investigators.

AMG 145 should be stored protected from light and according to the storage and expiration information provided on the label. AMG 145 should be handled per the instructions provided in the IPIM and the Instructions for Use (IFU) for the prefilled AI/pen or Personal Injector. The prefilled AI/pen or Personal Injector should be checked for damage that may occur during shipment or if not handled properly. Damaged product should not be used. Further details are provided in the IPIM and IFU.

The lot number of investigational product should be recorded on each subject's Drug Administration Case Report Form.

6.1.1 Dosage, Administration, and Schedule

IP will be administered SC in accordance with instructions in the IPIM.

IP administration at each on-site visit must be done after vital signs and blood draw procedures, as applicable. The date, time, and amount (as designated by partial or full injection of AMG 145) will be recorded on the individual subject's worksheet and/or electronic Case Report Form (eCRF). After IP administration on Day 1 or Week 48 for subjects initially randomized to standard of care (SOC)-alone, subjects should be kept for observation for at least 30 minutes before being discharged.

On Day 1 of the study, subjects randomized to AMG 145 plus SOC will be trained on self-administration of study drug and will self-administer IP at the investigational site,

under the supervision of a healthcare provider. Subjects without prior experience of self-injection of AMG 145 will subsequently visit the site to self-administer AMG 145 at Week 2 (Q2W regimen only), Week 4 (Q2W and QM regimens) and Week 8 (QM regimen only). After the Week 4 visit for subjects on Q2W regimen or Week 8 visit for subjects on QM regimen, IP can be administered at a location external to the study site, using the prefilled AI/Pen or Personal Injector provided. Thereafter, AMG 145 will be self-administered or administered by a caregiver at home.

The subject (or designee) must have demonstrated competency in administration of SC injections before self-injection will be permitted. For subjects that prefer not to self-administer IP, IP may be administered at the site.

Subjects will receive training on IP use prior to home administration; however IP may be administered at the site if subjects prefer not to self-inject AMG 145.

Subjects randomized to AMG 145 + SOC and selecting Q2W IP administration will receive a total volume of 1.0 mL via 1 prefilled AI/pen injection every 2 weeks.

Subjects randomized to AMG 145 + SOC and selecting QM IP administration will receive a total volume of 3.0 mL monthly via 3 separate prefilled AI/pen injections or a total volume of 3.5 mL via a single Personal Injector. Injection sites should be rotated throughout the study. For the AI/pen, the SC injections should be administered in a consecutive fashion with all injections completed within 30 minutes.

The dosing schedule is also described by a [schema](#) in the protocol synopsis.

For further details regarding IP administration procedures, the IPIM should be consulted.

6.1.2 Dosage Adjustments

Dose adjustments of background lipid lowering therapy during the study are discouraged, but will be permitted for subjects that experience intolerable adverse events. If an investigator wants to make a dose adjustment they must contact the medical monitor prior to doing so. All background therapy adjustments must be clearly documented and recorded on the appropriate eCRF page and in the source documents.

Subjects who are Late for a Scheduled Dose of Investigational Product

If a subject is late for administration of IP, administration should occur as soon as possible. A QM dose of IP should not be administered within less than 7 days of a previous dose. If a QM subject arrives for a scheduled visit and IP was administered within the prior 7 days, the dose should not be administered but all other study

procedures should be conducted and administration of IP should occur as soon as possible at least 7 days after the previous administration. If 2 Q2W doses have been administered within 7 days of each other, any subsequent dose should occur at least 7 days after the most recent dose.

6.1.3 Criteria for Withholding of Investigational Product

Reports from the central laboratory after each visit must be reviewed on receipt. If abnormalities that would preclude further dosing are noted, subjects should be called at home and instructed to withhold further dosing and scheduled to return for an ad hoc visit.

6.1.3.1 Elevation of Creatine Kinase (CK)

If CK is > 5x upper limit of normal (ULN), CK must be retested before IP is administered. The following rules apply:

CK at prior visit	CK on retest	Investigational Product Administration
> 5x ULN	> 10x ULN	Discontinue IP ^a Contact Amgen Medical Monitor
	>5x to ≤ 10x ULN	Consider continuing IP if alternative explanation
	≤ 5x ULN	Consider continuing IP

^a CK elevations >10x ULN that have been confirmed to be secondary to myocardial infarction do not require discontinuation of IP

6.1.3.2 Elevation of Liver Function Tests

Subjects with abnormal hepatic laboratory values (eg, alkaline phosphatase [ALP], AST, ALT, total bilirubin [TBL] or international normalized ratio [INR]) or signs/symptoms of hepatitis may meet the criteria for withholding of IP.

IP must be discontinued and the subject should be followed according to the recommendations in [Appendix B](#) (Additional Safety Assessment Information) for possible drug-induced liver injury (DILI), if ALL of the criteria below are met:

- TBL > 2x upper limit of normal (ULN) or INR > 1.5

AND

- AST or ALT > 3x ULN

AND

- no other cause for the combination of laboratory abnormalities is immediately apparent; important potential causes for abnormal AST/ALT or TBL values include, but are not limited to:
 - Obstructive gall bladder or bile duct disease
 - Viral or alcoholic hepatitis (eg, Hepatitis A/B/C/D/E, Epstein-Barr Virus, cytomegalovirus, Herpes Simplex Virus, Varicella)
 - Progression of malignancy involving the liver (note that metastatic disease to the liver, by itself, should not be used as an explanation for significant AST/ALT elevations)
 - Hypoxic or ischemic hepatopathy or congestive hepatopathy in association with significant right sided heart failure
 - Concomitant administration of other hepatotoxins, including drugs that inhibit bilirubin glucuronidation (eg, indinavir, atazanavir, irinotecan) or herbal or dietary supplements
 - Heritable disorders causing impaired glucuronidation (eg, Gilbert's Syndrome); alpha-one antitrypsin deficiency
 - Autoimmune hepatitis
 - Nonalcoholic steatohepatitis (NASH) or other "fatty liver disease"

IP should also be withheld and the subject should be evaluated for DILI if ANY of the following criteria are met:

- AST or ALT > 8x ULN at any time
- AST or ALT > 5x ULN but < 8x ULN for ≥ 2 weeks
- TBL > 3x ULN at any time
- ALP > 8x ULN at any time
- Clinical signs or symptoms that are, in the opinion of the investigator, consistent with hepatitis (such as right upper quadrant pain/tenderness, fever, nausea, vomiting, jaundice, rash or eosinophilia > 5%). If such signs or symptoms are coupled with ALT or AST elevations > 3x ULN, IP should be withheld.

If IP is withheld due to any of the conditions above, the subject should be followed according to recommendations in [Appendix B](#) for possible DILI.

6.1.3.3 Criteria for Rechallenge of AMG 145 After Potential Hepatotoxicity

The decision to re-challenge the subject should be discussed and agreed upon unanimously by the subject, Principal Investigator, and Amgen.

If signs or symptoms recur with re-challenge, then AMG 145 should be permanently discontinued. Subjects who clearly meet the criteria for permanent discontinuation should never be re-challenged.

6.1.3.4 Elevation of Triglycerides

If triglycerides are > 1000 mg/dL(11.3 mmol/L), the investigator will be informed and a repeat fasting triglyceride repeat test will be requested. If the retest confirms triglycerides > 1000 mg/dL(11.3 mmol/L), the Amgen medical monitor and the investigator will be informed so that appropriate medical follow up for the subject can be initiated.

6.2 Product Complaints, Including Device Complaints

A product complaint is defined as any written, electronic, or oral communication that alleges deficiencies related to the identity, quality, durability, reliability, safety, effectiveness, or performance of a drug or device after it is released for distribution to market or clinic by either Amgen or by distributors and partners for whom Amgen manufactures the material.

Any complaints associated with an investigational product(s) or non-investigational product(s) or device(s) supplied by Amgen are to be reported according to the instructions provided in the IPIM.

Concerns or irregularities about the packaging, appearance or usage of the prefilled AI/pen or Personal Injector are to be reported to Amgen within 24 hours of discovery or notification of the concern or irregularity. Should any such concerns or irregularities occur please do not use the prefilled AI/pen or Personal Injector until Amgen confirms that it is permissible to use.

Examples of potential product complaints that need to be reported to Amgen include, but are not limited to:

- broken container or cracked container,
- subject or healthcare provider cannot appropriately use the product despite training (eg, due to malfunction of the prefilled AI/pen or Personal Injector),
- missing labels, illegible labels, incorrect labels, and/or suspect labels,
- change in IMP appearance, for example color change or visible presence of foreign material,
- unexpected quantity or volume, for example amount of fluid in the prefilled AI/pen or Personal Injector, or
- evidence of tampering or stolen material.

If possible, please have the prefilled AI/pen or Personal Injector available for examination when making a product complaint. Maintain the prefilled AI/pen or Personal

Injector at appropriate storage conditions until further instructions are received from Amgen.

The investigator is responsible for ensuring that all product complaints observed by the investigator or reported by the subject that occur after signing of the ICF through 30 days after the last dose of IP or EOS, whichever is later, are reported to Amgen within 24 hours of discovery or notification of the product complaint.

For more details regarding the identification and reporting of product and device complaints, refer to the IPIM and the IFU.

6.3 Concomitant Therapy, Physical Exercise, and Diet

Throughout the study, investigators may prescribe any concomitant medications or treatments deemed necessary to provide adequate supportive care except for those listed in [Section 6.4](#). Background lipid lowering concomitant medications should be stable throughout study participation.

Subjects should maintain baseline level of exercise during the first year of study participation. Subjects will be required to refrain from unaccustomed intensive exercise (eg, heavy lifting or long runs) 48 hours prior to each visit.

6.4 Excluded Treatments During Study Period

The use of magnesium or aluminum hydroxide-containing antacids is not recommended within the period of two hours before and two hours after dosing with statins given the potential for interference with absorption.

7. STUDY PROCEDURES

Written informed consent must be obtained and will be implemented before protocol specific procedures are carried out. The risks and benefits of participating in the study will be verbally explained to each potential subject prior to entering into the study. The procedures to be performed at each clinic visit are described below and are summarized in [Appendix A](#) IP administered in clinic should not be administered until all study procedures are completed at each visit.

Subject visit schedule will differ based upon 3 factors: randomization, selection of Q2W or QM regimen, and prior experience with self-injection of AMG 145. Subjects randomized to AMG 145 + SOC without previous experience with self-injection of AMG 145 will have additional IP training visits at time of study start. At Week 48, a similar training schedule will be utilized for subjects randomized to SOC-alone at Day 1

with no previous experience with self-injection of AMG 145. All visits also apply to subjects randomized to SOC-alone unless otherwise specified.

7.1 General Study Procedures

7.1.1 Enrollment (EOS Parent Study/Day 1 OLE)

All efforts should be made to minimize any time gaps between completion of the parent study end of study (EOS) laboratory visit and Day 1 of the OLE visit. It is recommended that the Day 1 OLE visit occurs within 30 days of completion of the parent EOS laboratory visit. If the Day 1 OLE visit does not occur within 30 days of completion of the parent EOS laboratory visit, then all of the procedures detailed below will need to be repeated at the Day 1 OLE visit.

- Parent Study EOS lab visit procedures:
 - Medical History
 - Vital signs: sitting blood pressure (BP), heart rate (HR)
 - Review adverse events/ serious adverse events (AEs/SAEs)
 - Review concomitant medications
 - Body weight
 - Physical exam
 - Urine pregnancy (females of childbearing potential only)
 - Serum Follicle-stimulating hormone (FSH)(females deemed sterile or post-menopausal as defined above)
 - Urinalysis
 - Urine microalbumin
 - Hepatitis C virus (HCV) antibodies (Only in high risk subjects or if ALT or AST>2X ULN)
 - HCV viral load (in subjects positive for HCV)
 - Blood draw for fasting lipids (≥ 9 hour fasting sample), ApoA1, ApoB, chemistry, hematology, high sensitive C-reactive protein (hsCRP), Lp(a), HbA1c, and anti-AMG 145 antibodies; TSH

On Day 1 OLE, potential subjects will have the risks and benefits of participating in this study explained to them. Subjects will need to sign a new OLE ICF and will be evaluated against inclusion/exclusion criteria.

The following procedures will be performed during the Day 1 OLE visit:

- Medical History
- Cardiac History (If > 30 days from end of parent study)
- Vital Signs

- Weight
- Review AEs/SAEs
- Review concomitant medications
- Repeat parent EOS laboratory visit procedures if Day 1 OLE > 30 days from parent study EOS laboratory visit procedures (see above)
- Coagulation (PT/INR)
- Train subject on self-injection of AMG 145 if randomized to AMG 145 + SOC
- Observe subject self-inject AMG 145 at study site if randomized to AMG 145 + SOC (AMG 145 administration, must occur after completion of vital signs, if applicable, and blood draw procedures).
- Dispense IP for at-home injections (only for subjects who have previous experience of self-injecting AMG 145)

7.1.1.1 Week 2 (\pm 7 Days)–If Subject with no Previous Experience of Self-injection is Randomized to AMG 145 + SOC and Selects Q2W Regimen

- Vital signs: sitting blood pressure (BP), heart rate (HR)
- Review AEs/SAEs
- Review concomitant medications
- Train subject on self-injection of AMG 145
- Observe subject self-inject AMG 145 at study site (AMG 145 administration must occur after other procedures)

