Amgen Investigational Product Dosage and Administration: AMG 145 will be administered via subcutaneous injection using a spring-based prefilled 1.0 mL auto-injector/pen (AI/Pen) or when available, a 3.5 mL Personal Injector.

AMG 145 will be administered via 1 of 2 regimens:

- AMG 145 140 mg SC Q2W (1 prefilled AI/Pen injection) or
- AMG 145 420 mg SC QM (3 prefilled AI/Pen injections or 1 Personal Injector, once made available)

The 3.5 mL Personal Injector will only be made available for use in this study once it has been determined that the intended user population for AMG 145 can safely and effectively use the device in clinical trials under guidance of study investigators.

Upon completion of the Week 12 Visit, subjects will have the opportunity to switch between Q2W and QM every 3 months, provided the appropriate supply of IP is available.

Non Amgen Investigational Product Dosage and Administration: None.

Control Group: The control group comprises of subjects randomized to SOC-alone during the first 48 weeks of study participation. Until laboratory results are unblinded at Week 12, the control group should remain on stable lipid lowering therapy (eg, therapy prescribed in parent study or the same therapy prescribed before parent study participation whichever the subject is likely to tolerate). After unblinding at Week 12, investigators may prescribe any concomitant medications or treatments deemed necessary to provide adequate supportive care (Section 6.3). After 48 weeks of participation, these subjects will receive open-label AMG 145 in the regimen of their choice (Q2W or QM) and will no longer be considered part of a control group. These subjects may also switch between regimens every 12 weeks.

Procedures: Prior to enrolling in this study, subjects will need to undergo end of study (EOS) procedures for their qualifying parent study. In addition, subjects will need to sign a new study Informed Consent Form and meet inclusion/exclusion criteria requirements. Subject identification numbers will be the same as those in their parent protocols.

Subjects that fall within a 30 day window of completing the final laboratory assessments for a qualifying parent study do not require laboratory procedures to be repeated.

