Appendix A. Schedule of Assessments

Applies to both AMG 145 and SOC-alone groups unless specified otherwise					
Timepoint/Frequency	W116	W128	W140	W152	EOS Phone visit W156
General Procedures					
Vital Signs (sitting BP, HR)	X	X	X	X	
Review for AEs/SAEs	X	X	X	X	X
Concomitant therapy	X	X	X	X	X
Physical Exam				X	
Body Weight				X	
Laboratory					
Fasting lipids				X	
Chemistry, fasting glucose				X	
Hematology				X	
Coagulation (PT/INR)				X	
HbA1c				X	
Anti-AMG 145 antibodies				X	
HCV viral load ^l				X	
Urine pregnancy				X	
Investigational Product					
IP Dispense	X	X	X		
IP Reconcile	X	X	X	X	

Page 3 of 3

^a D1 = day of first administration of IP. This visit should also coincide with EOS visit for parent study; for visit windows see [Section 7](#) of the protocol. Procedures NOT conducted as part of EOS visit for parent study should be completed at this visit.

^b Training visit applies to subjects who are randomized to AMG 145 and select the Q2W regimen

^c Training visit applies to subjects who are randomized to AMG 145 and select QM regimen

^d Only if enrollment into 138 exceeds last laboratory visit from parent study by 30 days. Cardiac History Form will also need to be completed.

^e Telephone visit for subjects randomized to SOC-alone

^f Only for subjects receiving AMG 145 who have selected the QM regimen

^g Only for subjects receiving AMG 145 who have selected the Q2W regimen

^h Vitamin E samples will be drawn for all applicable visits, testing will be conducted by reflex when LDL-C is < 25 mg/dL

ⁱ Training visit applies to subjects who are randomized SOC-alone in year 1 and select the Q2W regimen in year 2

^j Training visit applies to subjects who are randomized SOC-alone in year 1 and select the QM regimen in year 2

^k Only for subjects randomized to placebo or SOC in parent study AND randomized to SOC-alone in Year 1

^l HCV antibodies only in high risk subjects (see [Section 7.1.2.4](#)) or if ALT or AST > 2x ULN; viral load only in subjects positive for HCV

^m FSH in applicable subjects for study entry only – see [exclusion criteria](#); urine pregnancy in females of childbearing potential

ⁿ Dispense IP for at-home injections (only for subjects who have previous experience of self-injecting AMG 145)

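### The pregnancy exclusion is judged on Day 1, but the urine test behind it may be up to 30 days old when Day 1 does not coincide with the parent study's final laboratory visit

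*Protocol*

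**What the plan says.** Exclusion criterion 3 (Protocol Section 4.2) covers this case: "Female subject is pregnant or breast feeding, planning to become pregnant or planning to breastfeed during treatment with IP". Section 7.1.1 places the eligibility decision on Day 1: "Subjects will need to sign a new OLE ICF and will be evaluated against inclusion/exclusion criteria".

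The entry pregnancy test is listed in Section 7.1.1 among the parent study's end-of-study laboratory procedures, as "Urine pregnancy (females of childbearing potential only". The separate Day 1 list does not include it. That list has only the conditional line "Repeat parent EOS laboratory visit procedures if Day 1 OLE > 30 days from parent study EOS laboratory visit procedures (see above".

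Two other places carry the allowance. The synopsis, under Procedures, says that subjects "within a 30 day window of completing the final laboratory assessments for a qualifying parent study do not require laboratory procedures to be repeated". Appendix A marks the Day 1 urine pregnancy entry with footnote d: "Only if enrollment into 138 exceeds last laboratory visit from parent study by 30 days".

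Subjects randomized to AMG 145 + SOC inject on Day 1. No pregnancy test is listed at Weeks 2, 4 or 8, either in Section 7.1.1 or in Appendix A. The next is at Week 12.

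Two passages limit the gap. Section 7.1.1 asks sites to keep the time between the parent laboratory visit and Day 1 as short as possible. Appendix A, footnote a, says that Day 1 should fall on the parent end-of-study visit, and that anything not done there should be done on Day 1.

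**The concern.** A 30-day carry-over is a reasonable economy for most entry laboratory values. Pregnancy differs because it is an exclusion in its own right and the status can change within the window. Where the two visits are separate but no more than 30 days apart, the plan asks the investigator to confirm criterion 3 on Day 1 without a current test.

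At stake is subject safety and the verification of an eligibility criterion. A site that follows the protocol exactly could randomize and dose a woman who meets exclusion 3. The protocol itself treats pregnancy as important: it is a reason for stopping investigational product (Section 8.1), it must be reported within 24 hours, and monitoring continues for 15 weeks after treatment (Section 9.3). No endpoint, analysis set or estimate depends on this point.

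**Working it through.** The plan states no figure to reproduce. The check is a reading of the schedule plus day counts.

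**Inputs**
- Carry-over limit: 30 days (Section 7.1.1; synopsis, Procedures; Appendix A, footnote d).
- First dose in this study, AMG 145 + SOC: Day 1 (Section 7.1.1).
- Next scheduled pregnancy test: Week 12, ± 7 days (Section 7.1.1.7; Appendix A).
- Assumption: the test was done at the parent end-of-study laboratory visit, as Section 7.1.1 implies. The parent protocols are not available here.

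**Age of the test at the first dose in this study**

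Let A = Day 1 date − date of the parent end-of-study laboratory visit.
- A = 0 (visits coincide): the test is 0 days old.
- A from 1 to 30 days: no repeat is required, so the test is A days old, at most 30.
- A > 30 days: the test is repeated on Day 1, so it is 0 days old.

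Only the middle case is affected. Testing on Day 1 in that case would bring the age from A to 0, a gain of at most 30 days.

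**Time from Day 1 to the next test**

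12 × 7 = 84 days, or 77 to 91 days with the ± 7-day window. A Day 1 test leaves this unchanged.

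**Is there a Day 1 safeguard elsewhere?**

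Vital signs, body weight and PT/INR are on the Day 1 list whatever the gap, and Appendix A marks them without footnote d. So the protocol already exempts some procedures from the carry-over, but not the pregnancy test. No passage requires a pregnancy test on Day 1 when A is 1 to 30 days.

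**Do the passages count the 30 days to the same date?**
- Section 7.1.1 counts to the Day 1 visit.
- Appendix A, footnote d, counts to enrollment.
- Section 5 defines enrollment as completion of the parent end-of-study visit plus a signed consent form. SAP Section 5.1 dates it as the later of those two events and defines Study Day 1 separately, as the first dose for treated AMG 145 + SOC subjects.

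Section 7.1.1 has consent signed on Day 1. If that is followed, the two counts agree. If consent was signed k days before the first dose, footnote d would accept a test up to 30 + k days old, where Section 7.1.1 would require a repeat. The documents give no distribution of k.

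**The case against.** The strongest counter-argument is that the 30-day rule is a consistent, deliberate choice, and that the intended gap is zero. Footnote a and the instruction to shorten the gap both point that way. Exclusion criterion 2 also requires effective contraception during treatment and for 15 weeks afterwards. Scheduled tests are not the only route to detection: medical history and adverse events are reviewed on Day 1. All of this lowers the risk and makes 30 days a ceiling. It does not close the gap, because Section 7.1.1 expressly allows separate visits and contraception does not verify criterion 3.

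Three stronger readings are tempting, and the documents do not support them.
- **Unequal protection of the arms.** SOC-alone women take their first dose in this study at Week 48, a visit that includes a pregnancy test. That test is routine for both arms. Section 7.1.2.4 sends on-study laboratory samples to the central laboratory, and no passage requires the result before dosing.
- **A 121-day interval covering six Q2W doses.** The longest interval between tests at entry is 30 + 84 + 7 = 121 days, but 84 + 7 = 91 of those days follow Day 1 and would remain after the fix. The schedule accepts longer intervals later: Week 24 to 48 is 24 × 7 = 168 days, and Week 104 to 152 is 48 × 7 = 336 days.
- **First exposure to the drug.** The SAP's four-level treatment grouping (Section 5.3) includes subjects who had AMG 145 in the parent study and again here, so for some women Day 1 is not the first exposure.

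**Conclusion.** The point holds in a limited form. When Day 1 is separate from the parent end-of-study laboratory visit but within 30 days of it, exclusion 3 is confirmed on a urine test up to 30 days old, and no further test is scheduled until Week 12. The avoidable part is at most 30 days under Section 7.1.1. Under footnote d it could be longer if enrollment preceded the first dose.

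The number of women affected cannot be estimated. The documents give neither the number of women of childbearing potential nor the distribution of roll-over gaps. The change would still have had subjects to act on when the protocol was written: Section 10.2 expected about 950 more to enroll (4428 − 3478). This is a cheap improvement, between optional and recommended, and it does not affect the validity of the analysis.

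**What to change.** 1. In Section 7.1.1, add a urine pregnancy test for women of childbearing potential to the standing Day 1 list, whatever the time since the parent laboratory visit. A test done the same day, because the visits coincide, would satisfy it.
2. In Appendix A, remove footnote d from the urine pregnancy test in the Day 1 column. That row also holds FSH, so split the row or give the two tests separate footnotes. FSH keeps the carry-over.
3. In the synopsis, under Procedures, name the pregnancy test as the exception to the 30-day allowance.
4. State that this test is read at the site, before eligibility is confirmed for randomization. Without that, Section 7.1.2.4 implies central processing, and the result might not be available when criterion 3 is judged.
5. Reconcile footnote d with Section 7.1.1 so that both count the 30 days to the same date.

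Leave the carry-over in place for all other laboratory tests.

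The cost is one urine kit and a few minutes, only for women of childbearing potential whose Day 1 does not coincide with the parent laboratory visit, at a visit that already takes place.
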